## **Objective**

To evaluate the effect of communicating multiple sources of uncertainty about the benefits and harms of new drugs on participants' decisions.

## **Study design and randomization**

In this randomized controlled trial using a pre-post study design, participants will be randomized with equal allocation to 1 of 5 groups. The control group will receive information about a new cancer drug's benefits and harms; the intervention groups will also be given brief statements about sources of uncertainties with the drug's evidence (1, 2, 3, or 4 sources of uncertainties).

## **Participants**

We will recruit a nationally representative sample of US adults to participate in this study. Eligible participants will be above 18 years of age and fluent in English. Participants will be recruited through CloudResearch, a market research company which engages with hundreds of research panel providers that use various methods for recruitment. Eligible participants were not allowed to have participated in the earlier survey, which we verified through unique participant identifiers assigned to each participant from the survey company.

Participants will be asked for informed consent before initiating the survey. No identifying information about participants will be asked or known by the study team, and CloudResearch will not have access to the participants' responses.

## **Intervention**

We developed brief statements to communicate the most common sources of uncertainties with new cancer drugs cited in FDA approval decisions and the scientific literature. In the first study, we evaluated the effect of communicating different individual sources of uncertainties on participants' hypothetical decisions. In this second trial, we will evaluate the additive effect of communicating multiple sources of uncertainties.

Given the combinations of uncertainties that could have been tested in this trial, we will focus on the sources of uncertainties that had the largest effects on participants' decisions in the first trial. Therefore, participants randomized to receive 2 sources of uncertainties received the 2 that had the largest effects in the first trial, and so forth. **Table 1** presents the combinations of statements that will be tested in this trial.

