## **Primary outcome**

The primary outcome is the pre-post change in participants decisions to take the new cancer drug in each experimental condition relative to the control group. Decision-making was

measured using a 4-point Likert scale: very likely, somewhat likely, somewhat unlikely, and very unlikely. For the primary analysis we will categorize participant responses as binary and focus on participants who changed their decisions from likely (pre-intervention) to unlikely to take the drug (post-intervention).

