### **Secondary outcomes**

Secondary outcomes will compare participants' understanding of uncertainties, perceptions, and emotions after learning about a source of uncertainty relative to the difference in the control group. We will also assess trust associated with communicating uncertainty.

For understanding (measured on a 4-point Likert scale: strongly disagree to strongly agree), we will compare the percentage of participants who improved their understanding of the drug after being randomized to a source of uncertainty. For perceptions (measured on a 4-point Likert scale: very uncertain to very certain), we will compare the percentage of participants who were less certain that the drug would work well after learning about a source of uncertainty, and for emotions (measured on a 4-point Likert scale: extremely worried to not worried at all), we will compare the percentage of participants that were more worried about taking the drug after learning about a source of uncertainty. To assess trust, we will ask participants about their perceived trust in the information and the source of the information (measured on a 4-point Likert scale: not at all trustworthy to very trustworthy), and whether learning about uncertainties made them more or less trusting in the FDA (measured on a 4-point Likert scale: less trusting to more trusting).

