### **Statistical analysis**

For the primary analysis comparing differences between the experimental conditions and the control group, we will use generalized estimating equations. To compare differences between groups in trust, which was only measured post-intervention, we will use  $\chi^2$  tests. As a sensitivity analysis we will use the  $\chi^2$  test (or Fischer's exact test as appropriate) to evaluate the percentage difference between groups in participants who were likely to take the drug post-intervention. To provide comparable estimates of the within group differences (changes from pre to post responses) for the trial, we will use McNemar's  $\chi^2$  test for paired data.

We powered the trial to detect a between group difference of 10% (65% post intervention for control vs 55% post intervention for the experimental groups) based on findings from the first trial, with 90% power and a two-sided alpha of 0.05. We aimed to recruit 600 participants per group in case of dropouts or errors during survey completion.

We plan to exclude participants who complete the survey in less than 150 seconds, a conservative cutoff that is consistent with other studies. We will also exclude participants who do not complete the survey and who provide straight-line responses.

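### The plan states an additive aim and nests the arms for it, but names no contrast that estimates what a further statement adds

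*Combined protocol and SAP*

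**What the plan says.** The Objective is broad: "To evaluate the effect of communicating multiple sources of uncertainty about the benefits and harms of new drugs". The Intervention section is more specific. It contrasts this trial with a first one on individual sources and then says: "In this second trial, we will evaluate the additive effect of communicating multiple sources of uncertainties".

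The arms are built for that aim. The Intervention section says "participants randomized to receive 2 sources of uncertainties received the 2 that had the largest effects in the first trial", and so on upward. Table 1 confirms the nesting: small magnitude of effect; then limited study population added; then unvalidated surrogate endpoint; then limited study duration.

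The planned comparisons are these:

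- **Primary outcome:** "pre-post change in participants decisions to take the new cancer drug in each experimental condition relative to the control group", made binary with a "focus on participants who changed their decisions from likely (pre-intervention) to unlikely to take the drug (post-intervention)".
- **Secondary outcomes** (understanding, perceptions, emotions): "after learning about a source of uncertainty relative to the difference in the control group".
- **Primary analysis** (Statistical analysis section): "For the primary analysis comparing differences between the experimental conditions and the control group, we will use generalized estimating equations".
- **Trust and sensitivity analyses:** χ² tests between groups, with no pair, trend or contrast named. The sensitivity test uses post-intervention answers only.
- **McNemar's test:** change within each group.
- **Power:** one case, "65% post intervention for control vs 55% post intervention for the experimental groups", at 90% power and two-sided 0.05, with 600 recruited per group.

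**The concern.** With nested arms, the contribution of each further statement is the difference between neighbouring arms: 2 vs 1, 3 vs 2, 4 vs 3. A trend across the 1- to 4-statement arms summarises the three steps. The plan names none of these and gives no interval for any of them.

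Four effects against control are a different quantity. All four can be significant when only the first statement matters. Equally, one arm reaching significance while its neighbour does not is no evidence of a step. A report that follows the plan could therefore show four significant results and describe them as additive without any planned analysis behind the word. Contrasts chosen after the results are seen would carry less weight than contrasts named in advance.

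**Working it through.** **Inputs from the plan** (Statistical analysis section): 65% control, 55% experimental, 90% power, two-sided 0.05, 600 recruited per group. **Assumed:** all step sizes between experimental arms, which the documents do not give. The calculations use post-intervention proportions, as the plan's own power case does.

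**1. The plan's own figure.** With pooled null variance,

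n = [1.960·√(2·0.60·0.40) + 1.282·√(0.65·0.35 + 0.55·0.45)]² / 0.10² = 502.3, so 503 per arm.

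With all 600 evaluable, power is Φ[(0.10 − 1.960·0.02828)/0.02814] = 0.943. The target of 600 is consistent with 503 plus an allowance of 1 − 503/600 = 16%; the plan states no rate. I use 503 and 600 as the range. This calculation covers one comparison with control and sets no difference between experimental arms.

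**2. What four comparisons with control show if later statements add nothing.** Take control 65% and all four arms 55%. If the comparisons were independent, all four would be significant with probability 0.900⁴ = 0.66 (503) or 0.943⁴ = 0.79 (600). The shared control correlates them and raises this. Simulation (400,000 trials) gives 0.74 and 0.84.

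**3. What a step estimate needs.** The difference between two control-referenced effects is p₂ − p₁; the control term cancels. Its standard error is √[p₁(1−p₁)/n + p₂(1−p₂)/n], which cannot be read off the two intervals against control. For an assumed step from 55% to 52.5%:

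| | 503 per arm | 600 per arm |
|---|---|---|
| SE | 0.0314 | 0.0288 |
| 95% half-width | 6.2 points | 5.6 points |
| Power, Φ(0.025/SE − 1.960) + Φ(−0.025/SE − 1.960) | 0.125 | 0.140 |
| Step from 55% needed for 80% power | 8.8 points | 8.1 points |

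**4. Trend across arms 1-4,** weights (−3, −1, 1, 3), SE = √[Σw²p(1−p)/n].

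- Equal 2.5-point steps (55, 52.5, 50, 47.5%): L = −1.65 − 0.525 + 0.50 + 1.425 = −0.25. SE is 0.0994 (503) or 0.0910 (600), and power is 0.71 or 0.78.
- No increment: it rejects in 5% of trials, as it should. A trend over all five arms rejects in 82% (503) to 88% (600) of the same trials, because it picks up the gap between control and the first statement. Control has to be left out.
- Steps of 7.5, 0 and 0 points: L = −0.225, and the trend still rejects in 62% (503) to 70% (600) of trials although statements 3 and 4 add nothing. The trend therefore needs the adjacent intervals beside it.

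**5. Multiplicity.** With all four arms at 55%, at least one of the trend and the three adjacent intervals excludes zero in about 17% of trials, at either sample size.

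**6. If the outcome is one likely-to-unlikely switch per person.** I assumed a control switch rate of 3-10%, 10 points more in each arm, and as denominator either everyone or the 65% assumed likely at baseline. All four arms are then significant in 86-100% of no-increment trials, and adjacent power at 2.5-point steps is 11-24%. The conclusion does not change.

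**The case against.** The strongest reply is that the point hangs on one word. Additive appears once, in a descriptive sentence set against the first study's individual sources, and may only mean the combined effect of several statements. The Objective, Primary outcome and primary analysis agree with one another and are met by comparisons with control. That stands, and it rules out a stronger reading: the documents do not support saying that the trial fails its objective or that its primary analysis is invalid. It does not remove the gap, because the sentence says what this trial is for and Table 1 is built in single-statement steps.

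The χ² tests between groups are not limited to control. True, but an overall test across groups would not isolate a step, and no pair is named.

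A reader might infer that a real step could never be told from noise. That goes too far. The arms are independent randomized groups, and with arm-level counts anyone could compute an interval for the post-intervention proportion or the switch. What is lost is prespecification.

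A reader might also infer from the single 55% that the planners expect no increment. The documents do not say so; the flat pattern is used here only as a scenario.

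Finally, single steps are poorly powered. That is a reason to present them as estimates, not to omit them.

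**Conclusion.** The point holds as a mismatch between the aim in the Intervention section and the Statistical analysis section. The plan names no incremental contrast, so results obtained as planned cannot by themselves support a statement about what a further statement adds. In the flat scenario, four significant comparisons with control would occur in 74-84% of trials.

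That the contrast is absent follows from the text alone. The sizes rest on the plan's 65% and 55%, on 503 to 600 evaluable per arm, and on assumed steps. They use post-intervention proportions; a GEE on paired answers could have more or less power, depending on a pre-post correlation that the documents do not give.

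Neither the nested arms nor the added contrasts can establish strict additivity. Statements 2 to 4 are never given alone in this trial, and the order is fixed. The gap should be fixed, but it leaves the primary comparisons intact.

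**What to change.** 1. **Add secondary contrasts on the primary outcome to the Statistical analysis section.** Suggested text:

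> As a secondary analysis of what further statements add, we will test a linear contrast (−3, −1, 1, 3) across the 1-, 2-, 3- and 4-statement arms, without control, at two-sided 0.05. We will report 2 vs 1, 3 vs 2 and 4 vs 3 as percentage-point differences with 95% confidence intervals.

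 The plan gives no GEE terms or link. State whether these are arm-by-time contrasts on pre and post answers or arm contrasts on the switch. If the link is not the identity, take the differences from model-predicted proportions.
2. **State the multiplicity rule.** Name the trend as the only test and present the adjacent differences as estimates with unadjusted intervals, or else adjust them. Say that a significant trend does not show that every step adds something.
3. **State the limits of power.** The 90% for 10 points applies to a single comparison with control. Single-step power is low: 12-14% at an assumed 2.5 points, with an interval half-width of about 5.6-6.2 points.
4. **Reword the additive claim in every case.** Refer to the incremental effect of adding the named statement in this fixed order. If the contrasts are not added, say instead that each set of statements is compared with control.
5. **If data collection has begun,** label the contrasts as added later.

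The cost is a few sentences and four secondary contrasts, with no more participants, arms or survey items. The downsides are slightly more analysis and an open admission of low power for single steps. Rewording alone costs one sentence but gives up the incremental question.

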## **Procedure**

At the start of the survey, participants will be given a vignette describing a 38-year-old woman that was recently diagnosed with non-small cell lung cancer. The woman's doctor tells her about a new drug that was approved by the FDA for her disease and that is covered by her insurance. Participants will then be presented with a table summarizing the main benefits and harms of the drug, which was developed using the FDA's Drug Trials Snapshot for adagrasib.

In the pre-intervention phase, we will ask participants about how likely they would be to take the drug if they were in Alex's position, how certain they are that the drug will work, and how worried they would feel about taking the drug. We will also assess their understanding of the drug's benefits and risks. Participants will then be randomized to 0, 1, 2, 3 or 4 statements about sources of uncertainty with the drug's evidence. The post-intervention questions will re-assess decision-making, perceptions, emotions, and understanding, as well ask participants about their trust in the information that they were given, and the FDA.

## **Primary outcome**

The primary outcome is the pre-post change in participants decisions to take the new cancer drug in each experimental condition relative to the control group. Decision-making was

measured using a 4-point Likert scale: very likely, somewhat likely, somewhat unlikely, and very unlikely. For the primary analysis we will categorize participant responses as binary and focus on participants who changed their decisions from likely (pre-intervention) to unlikely to take the drug (post-intervention).

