## PRE-INTERVENTION QUESTIONS

### **Section B: Decision making**

4. Imagine you were Alex and diagnosed with non-small cell lung cancer. How likely are you to take the new drug, Zenova?
  1. Very unlikely
  2. Somewhat unlikely
  3. Somewhat likely
  4. Very likely

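### Every stated analysis of the decision item uses the likely/unlikely cut, and the one between-group sensitivity analysis also ignores the pre response, so it cannot test dependence on the cut-point

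*Combined protocol and SAP*

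**What the plan says.** Under Primary outcome the decision is "measured using a 4-point Likert scale: very likely, somewhat likely, somewhat unlikely, and very unlikely". Sections B and F of the survey ask it on that scale before and after the additional information. The outcome is defined as a change: "The primary outcome is the pre-post change in participants decisions to take the new cancer drug in each experimental condition relative to the control group". The scale is then cut: "For the primary analysis we will categorize participant responses as binary", with the focus on people who move from likely to unlikely.

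The Statistical analysis section states three analyses that bear on this item:

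- Primary, between groups: "we will use generalized estimating equations". Link, terms and covariates are not given.
- Sensitivity, between groups: a chi-square or Fisher test "to evaluate the percentage difference between groups in participants who were likely to take the drug post-intervention".
- Within group: McNemar's test on paired pre and post responses.

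No ordinal, mean-score or any-step analysis of the decision item is stated. For perceptions and emotions, by contrast, the Secondary outcomes section counts people who became less certain or more worried, which can register a one-step move.

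**The concern.** A participant who goes from very likely to somewhat likely, or from somewhat unlikely to very unlikely, counts as unchanged in every stated analysis of the decision.

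A sensitivity analysis should vary a debatable choice and show whether the conclusion survives. Here the debatable choice is the cut-point, and the sensitivity analysis keeps it. What it changes is to set aside the pre response, which is the main asset of a pre-post design.

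The Intervention section gives the aim as the additive effect of several statements. If the arms with two, three or four statements look alike on the binary outcome, that could be a true plateau or a softening within the likely half. No stated analysis of the decision item separates the two.

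**Working it through.** **1. The plan's own figure.** Inputs from Statistical analysis: 65% vs 55%, two-sided alpha 0.05, power 90%. With mean proportion 0.60,

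n = [1.960·√(2·0.60·0.40) + 1.2816·√(0.65·0.35 + 0.55·0.45)]² / 0.10²
= [1.358 + 0.883]² / 0.01 ≈ 502.3, so 503 per group.

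The target of 600 leaves room for 1 − 503/600 = 16.2% loss (no loss rate is stated) and gives 94.3% power with no loss. The post-only comparison meets its target at the design effect.

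**2. A smaller effect, closed form.** For 65% vs 59% with 500 analysable per arm (an assumption), the post-only test has

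z = [0.06·√500 − 1.960·√(2·0.62·0.38)] / √(0.65·0.35 + 0.59·0.41) = (1.3416 − 1.3454)/0.685 ≈ −0.01,

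that is, about 50% power.

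**3. The same effect by simulation, spread over the scale.** The documents give no category split and no pre-post correlation, so both are assumed: pre responses 15/20/40/25% from very unlikely to very likely (65% likely), a normal latent response before and after, and a uniform latent shift that takes 65% to 59% likely; 500 per arm. Power by latent correlation:

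| Analysis | 0.5 | 0.7 | 0.8 |
|---|---|---|---|
| Likely-to-unlikely responder | 34% | 39% | 44% |
| Post-only binary (planned sensitivity test) | 50% | 52% | 51% |
| Binary pre-post change, arm by time | 40% | 51% | 58% |
| Binary post, adjusted for 4-level pre | 56% | 65% | 69% |
| 4-level post score, adjusted for pre | 73% | 84% | 92% |

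Repeat runs differ by up to about 3 points. A proportional-odds fit at correlation 0.7 gave 85%, in line with the score analysis. At that correlation, moving from the post-only test to the baseline-adjusted binary analysis gains about 13 points (52% to 65%), and using all four levels gains about 19 more (65% to 84%).

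**4. The scale alone, without the pre response.** The odds ratio implied by 65% vs 55% is (0.65/0.35)/(0.55/0.45) = 1.52. Under proportional odds, a post-only four-level analysis needs 388 to 476 per group over a range of assumed splits, against about 501 for the binary version of the same formula: a saving of 5% to 23%.

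**5. Where the movement occurs.** A second simulation used the same pre split, 600 per group, and 5% background movement one step in each direction. The first two rows have a 5-point net effect at the midpoint. The third applies the same step probability within the halves only, so nothing extra crosses the midpoint.

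| Movement | Post-only binary | Binary pre-post change | 4-level, adjusted for pre |
|---|---|---|---|
| One step down everywhere | 42% | 97% | 100% |
| Across the midpoint only | 43% | 97% | 77% |
| Within halves only | 5% | 5% | 85% |

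Binary pre-post power is much higher here than in step 3 because responses are assumed far more stable in the absence of an effect. The size of any loss therefore depends on quantities the documents do not supply.

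**The case against.** The strongest defence is that nothing here is an error. The outcome is a changed decision, the cut is at the scale's natural midpoint, and it is prespecified. The post-only test addresses the quantity the trial was sized on and is unbiased under randomization. All of that stands, and it is why the binary primary and the chi-square test should both stay.

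Four stronger readings are tempting, and the documents do not support them.

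- *A reader might infer that the primary analysis is underpowered.* Step 1 shows that the plan's calculation holds at its 10-point effect.
- *A reader might infer that the pre response is discarded throughout.* The primary outcome is a pre-post change analysed by GEE, and McNemar's test is paired. Only the sensitivity test drops it.
- *A reader might infer that cutting the scale always costs power.* Step 5 shows the reverse when movement is confined to the midpoint. The low responder figures also rest on one reading of a GEE whose terms are not stated; an arm-by-time contrast does better at every correlation examined.
- *A reader might infer that the increments between arms are known to be small and to begin within the likely half.* That is plausible, but nothing in the documents establishes it. Contrasts of each arm with control would not estimate those increments anyway.

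It is also fair that a latent correlation of 0.7 implies a lot of unprompted movement: about 12% of controls would go from likely to unlikely within one short survey. At 0.9, binary pre-post change reaches 73% power for the same 6-point effect. A uniform latent shift favours an ordinal model as well. Finally, the perception and emotion outcomes can register one-step moves, so the trial is not wholly blind to softening; but they measure something other than the decision.

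**Conclusion.** The concern holds in a limited form. All stated analyses of the decision item share one cut-point, and the single between-group sensitivity analysis neither varies that cut nor uses the pre response. It cannot show whether the conclusion depends on the cut.

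The loss is of sensitivity to effects below the design effect and to shifts within a half. Under the spread-effect assumptions of step 3 it is considerable (about 50% power against 73–92%). It is total if all movement stays within halves, and becomes a gain for the binary pre-post analysis if all movement crosses the midpoint. Because the pattern of movement is unknown in advance, the reasonable course is to prespecify both scales. This is an improvement that should be made, not a defect in the primary analysis.

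**What to change.** Leave the binary primary and the post-only chi-square test as they are. Add to Statistical analysis one prespecified sensitivity analysis: a proportional-odds model of the four-level post decision, with arm and the four-level pre decision (categorical) as covariates. Report odds ratios with 95% confidence intervals for each arm against control and for adjacent arms (2 vs 1, 3 vs 2 and 4 vs 3 statements), so that the analysis addresses the additive aim. Also report the 4x4 pre-post table for each arm, which lets readers see where movement occurred.

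The cost is one model and five tables on data already to be collected; no new questions or participants are needed. The drawbacks are the proportional-odds assumption and an effect measure less direct than a difference in percentages, both confined to this analysis. Specifying it beforehand also keeps a later ordinal analysis from looking data-driven.
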